Once the MTD is determined by the dose escalation phase, participants will be enrolled on the dose expansion cohort. Participants on the dose expansion cohort will receive 2 doses of CLR 131 with the first dose on day 1 followed by

the second dose on day 8, with the dose determined by the dose escalation phase.

SPECT/CT imaging will be performed on days 2, 3, 4-6, and 7-8 of the treatment period to visualize and quantitate the biodistribution of CLR 131. Based on these SPECT/CT imaging scans, the [name] lab will utilize the Monte Carlo method to predict absorbed dose of CLR 131 to tumors and normal structures.

All subjects will start thyroid-protection medication the day prior to the CLR 131 dosimetry test dose and will continue to take thyroid protection medication for 14 days after the last CLR 131 dose.

Based on the calculated absorbed dose of CLR 131 to the specific targeted tissue, the subject will undergo external beam radiation therapy (EBRT) to complete the designated radiation dose outlined in the re-irradiation plan, as per standard of care. Prior to CLR 131 administration and at 3 and 6 months post EBRT, subjects will be assessed for changes to swallow function. Prior to CLR 131 administration and at 3, 6 and 12 months post EBRT, quality of life measures and salivary characteristics will be assessed. We anticipate the total study (baseline, CLR 131 administration, EBRT and 3, 6, 12 and 24 month follow up assessments) to take 27 months per participant.

Study Duration: 47 months

[figure not shown]
Subject Participation Duration: 27 months

Estimated Time to Complete Enrollment: 20 months

Date Accrual Goal Met / Study Closed to Accrual April 18, 2022

Date DLT window completed by last participant June 16, 2022

Schematic of Study Design:

***Approximately 6 safety labs will coincide with SOC EBRT visits, and 6 safety lab visits will fall outside of the SOC EBRT visits.**

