3.2 Study Outcome Measures

3.2.1 *Primary*

- Incidence of adverse events assessed using Common Terminology Criteria for Adverse Events (CTCAE) version 5.0

3.2.2 *Secondary*

- Median radiation treatment time and median number of dose delays due to toxicity
- CLR 131 tumor uptake via SPECT/CT imaging and Monte Carlo calculations
- Overall response rate (ORR) defined as the proportion of subjects who experience either a partial response or complete response within 6 months post completion of EBRT as measured by standard of care imaging (e.g. CT, MR, PET-MR)
- Swallow function assessed by Dynamic Imaging Grade of Swallowing Toxicity (DIGEST) scale
- Quality of life (QoL) assessed by MD Anderson Dysphagia Inventory score (MDADI)
- Salivary flow rate related quality of life assessed by stimulated salivary flow

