5.5 Treatment Assignment Procedures

Subjects who agree to participate and who provide written informed consent will be enrolled via the University of Wisconsin Carbone Cancer Center (UWCCC) Oncore database by the Radiation Oncology research team prior to study-specific participation. All subjects must meet eligibility criteria as listed above. The research staff will verify eligibility, assign a case number, and register the subject in OnCore prior to study-specific participation. The following information will be recorded:

- Protocol number
- Subject's name
- Subject's medical record number
- Subject demographic data

The subject will also be registered with Collectar Biosciences to ensure drug product availability and shipment. Information to be provided to Collectar Biosciences includes: assigned subject identification number, initials, year of birth, body surface area, and dates of planned CLR 131 administration.

5.5.1 *Evaluable Subject*

For evaluation of safety endpoints, any subject that receives any portion of one treatment dose of CLR 131 will be included.

For evaluation of efficacy, subjects must receive all doses of CLR 131 in their entirety and at least one post-infusion efficacy assessment.

5.6 *Subject Withdrawal*

Treatment may continue as specified in the above treatment modality sections or until one of the following criteria applies:

- disease progression;
- intercurrent illness that prevents further administration of treatment;
- unacceptable adverse event(s) (as determined by the subject, treating physician)
- subject decides to withdraw consent for participation in the study;
- subject refuses further treatment (without withdrawing consent for study participation);
- general or specific changes in the subject's condition render the subject unacceptable for further treatment in the judgment of the investigator;
- new data related to the experimental agent which would suggest that continuing treatment on protocol would impose unwarranted potential risks beyond what was known at the time of treatment initiation.
- a female subject becomes pregnant

Subjects will be removed from protocol therapy and the site investigator notified when any of the criteria listed above apply. The reason for discontinuation of protocol therapy will be documented on the electronic case report form (eCRF).

5.6.1 *Handling of Subject Withdrawals or Subject Discontinuation of Study Intervention*

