14.2 Sample Size Considerations

An mTPI-2 design, an extension of modified toxicity probability interval (mTPI-2), will be used to identify the MTD using cohorts of 4 subjects and up to 3 dose levels of CLR 131 (Ji *et al.*, 2007; Ji & Wang, 2013). The first 4 subjects will be treated at Dose Level 1. The maximum number of subjects treated at a dose level will be 8, with one exception: if 1 out of 8 subjects experiences a DLT at Dose Level 1, the study team will consider the possibility of treating 2 additional subjects at Dose Level 1. The trial can be monitored using columns 4 and 8 of [Table 3](#) below, which contains the dose-escalation rules. Dose escalation will not be confirmed until all subjects in cohort recover to non-DLT levels or meet the criteria above. If 0 out of 4 subjects experiences a DLT at Dose Level 2, the study will move directly to the expansion phase.

Dose Level	Doses* of CLR 131
-1	12.5 mCi/m ²
1**	15.6 mCi/m ²
2	18.75 mCi/m ²

*Dose level listed is administered on first on day 1 and again on day 8.

**The first 4 subjects will be treated at dose level 1. Dose level -1 will be used as a de-escalation dose.

Table 3: Dose escalation rules

	1	2	3	4	5	6	7	8	9	10
0	E	E	E	E	E	E	E	E	E	E
1	D	D	D	S	S	S	S	S	S	E
2		DU	DU	D	D	D	S	S	S	S
3			DU	DU	DU	DU	D	D	D	D
4				DU	DU	DU	DU	DU	DU	D
5					DU	DU	DU	DU	DU	DU
6						DU	DU	DU	DU	DU
7							DU	DU	DU	DU
8								DU	DU	DU
9									DU	DU
10										DU

Column indicates the number of subjects treated. Row indicates the number of subjects with DLTs. **E**: Escalate to the next higher dose; **S**: Stay at the same dose; **D**: De-escalate to the previous lower dose; **DU**: De-escalate to the previous lower dose and the current dose will never be used again in the trial; sample size = **10**, target toxicity probability = **0.2**, epsilon 1 =**0.1**, epsilon 2 =**0.1**.

The number of participants treated in the expansion cohort is dependent on the number of participants treated at the MTD in the dose escalation phase using the the mTPI-2 design. Up to 12 subjects will be treated at the MTD. Statistical analysis for outcomes is based on participants treated at the MTD, including dose escalation patients treated at the MTD.

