14.3 Final Analysis Plan

14.3.1 Analysis of Primary Endpoints

Adverse events will be reported using frequency tables. Confidence intervals will be constructed using exact statistical methods (such as exact binomial confidence interval) due to small sample size.

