14.3.2 Analysis of Secondary Endpoints

Median radiation treatment time and median number of dose delays due to toxicity will be reported. CLR 131 tumor uptake via SPECT/CT imaging and Monte Carlo calculations will be reported. Quality of life measures (including swallow function assessed by DIGEST scale and

QOL assessed by MDADI score) will be analyzed using frequency tables and confidence intervals constructed using exact statistical methods (such as exact binomial confidence interval) or summary statistics. Comparison of continuous and categorical QOL measures before and after treatment will be described using summary statistics and analyzed using the Wilcoxon signed rank test and McNemar's test, respectively. ORR will be reported as a proportion with an exact confidence interval. Stimulated salivary flow will be reported before and after treatment using summary statistics.

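### When more than one dose level is used, Sections 5.5.1 and 14.2 give different sets for the primary adverse-event analysis, and Section 14.3.1 names none

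*Combined protocol and SAP*

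**What the plan says.** Section 3.2, the list of outcome measures, gives this as the only primary one: "Incidence of adverse events assessed using Common Terminology Criteria for Adverse Events (CTCAE) version 5.0".

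Section 5.5.1 defines who counts for safety: "For evaluation of safety endpoints, any subject that receives any portion of one treatment dose of CLR 131 will be included". It does not mention dose level.

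Section 14.2, after capping the MTD group at 12, says: "Statistical analysis for outcomes is based on participants treated at the MTD, including dose escalation patients treated at the MTD". It does not mention safety.

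Section 14.3.1, the primary analysis, has two sentences: "Adverse events will be reported using frequency tables" and "Confidence intervals will be constructed using exact statistical methods (such as exact binomial confidence interval) due to small sample size". Neither gives a population, a denominator or a layout by dose.

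The Protocol Summary records that accrual closed on April 18, 2022, and adds: "Date DLT window completed by last participant June 16, 2022".

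**The concern.** The primary table needs one denominator. Section 5.5.1 supplies one, Section 14.2 supplies another, and the section that should choose between them is silent. An analyst who follows Section 14.2 leaves out everyone treated at a level other than the MTD, and that can include a level abandoned because of toxicity. In a dose-finding trial those subjects carry much of the information on how toxicity relates to dose. Since enrolment and the DLT windows are over, the choice could also be made with the toxicity data in view.

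**Working it through.** **The plan's own figures.** The cap of 12 at the MTD comes from no formula, so there is nothing to reproduce. The escalation rules in Table 3 were rebuilt as an mTPI-2 design (uniform prior, target 0.2, interval 0.1 to 0.3, exclusion when the posterior probability of exceeding 0.2 is above 0.95). For 0 to 4 DLTs every cell agrees except 1 DLT in 1 subject. Columns 4 and 8, the ones the trial uses, agree for those rows.

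**Do the two rules meet on the same endpoint?** Section 14.2 speaks of outcomes, and Section 3.2 lists AE incidence among the outcome measures. Section 5.5.1 speaks of safety endpoints, and AE incidence is one. Both rules therefore reach the primary analysis.

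**How far apart are the sets?** Inputs from Section 14.2: cohorts of 4, start at Level 1, normally at most 8 per level during escalation, and direct expansion after 0 of 4 DLTs at Level 2. Assume 12 are reached at the MTD and that everyone counted received at least part of a treatment dose.

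- Only Level 1 used: 12 under both rules, so 0 of 12 dropped.
- 0/4 at Level 1 (escalate), 0/4 at Level 2, expansion at Level 2: 4 + 12 = 16 under 5.5.1 and 12 under 14.2, so 4/16 = 25% dropped.
- 0/4 at Level 1, 1/4 then 3/8 at Level 2 (de-escalate), Level 1 becomes the MTD: 12 + 8 = 20 against 12, so 8/20 = 40% dropped.

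Paths through Level -1 are not listed, so these cases are not a full range.

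**How likely is more than one level?** Leave aside the two optional extra subjects. Dosing then stays at Level 1 only after 1/4 DLT followed by 0 or 1 DLT in the next 4. For assumed true Level 1 DLT rates:

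- 10%: 0.2916 × 0.9477 = 0.276, so more than one level 72%
- 20%: 0.4096 × 0.8192 = 0.336, so 66%
- 30%: 0.4116 × 0.6517 = 0.268, so 73%

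If the two optional subjects are always added after 1/8, these become 88%, 78% and 79%.

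**Effect on incidence.** For any AE, the 5.5.1-set incidence minus the MTD-only incidence equals the fraction dropped × (incidence at the dropped levels − incidence at the MTD). Each percentage point of difference between levels therefore moves the result by 0.25 points (4 of 16) or 0.40 points (8 of 20). The documents give no figure for that difference. It may be positive, negative or close to zero.

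**Effect on precision alone.** Exact intervals, taking 95% two-sided because Section 14.3.1 states no level:

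- No events: upper limit 26.5% for 0/12, 20.6% for 0/16, 16.8% for 0/20.
- 25% incidence: 5.5–57.2% for 3/12, 7.3–52.4% for 4/16, 8.7–49.1% for 5/20.

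**The case against.** The strongest reply is that the two sentences do different jobs. Section 5.5.1 is a specific rule for safety. The Section 14.2 sentence is general, sits under sample size, follows directly on the cap of 12, and may only mean that escalation subjects at the MTD are pooled with the expansion cohort. On the usual principle that the specific rule prevails, all that is missing is a cross-reference in Section 14.3.1.

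That reading is reasonable, and it limits how serious the point is. It does not settle it. Section 3.2 counts AE incidence as an outcome measure. The Section 14.2 sentence is the only one in Section 14 that names an analysis set, and by admitting escalation subjects treated at the MTD it leaves the others out. No section states an order of precedence.

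It is also fair that the consequence is limited. The analysis is descriptive, with no test or decision threshold. AEs are recorded for every subject (Section 11.2), and the quarterly reports to the monitoring committee cover toxicities across the whole protocol (Section 12).

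A reader might infer more than the documents support:

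- **That the efficacy set conflicts too.** Section 5.5.1 says: "For evaluation of efficacy, subjects must receive all doses of CLR 131 in their entirety and at least one post-infusion efficacy assessment". This is a minimum condition. It combines with Section 14.2 as MTD subjects who also meet it, so nothing needs reconciling.
- **That dose delays have the same problem.** Section 14.3.2 says: "Median radiation treatment time and median number of dose delays due to toxicity will be reported". Section 3.2.2 lists this as a secondary outcome. No section calls it a safety endpoint or gives it a rival set, so summarising it at the MTD is a legitimate choice.
- **That the MTD-only table would understate toxicity.** Dropping a more toxic level lowers incidence, and dropping a less toxic one raises it. Section 11.3.2 expects Grade 3 mucositis and dermatitis from the external beam radiation, so common AEs may differ little between levels.
- **That the 5.5.1 set holds everyone given CLR 131.** It requires part of a treatment dose. Subjects who stop after the 15 mCi test dose are outside it, although Section 9 has those with inadequate uptake followed for safety and Section 11.2.1 records AEs from consent.

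**Conclusion.** The point holds. Once a second dose level is used, the plan contains two rules for the primary AE analysis that give different denominators, and nothing says which prevails. With 12 at the MTD, following Section 14.2 omits 4 of 16 or 8 of 20 subjects on the paths worked through, and none if dosing never leaves Level 1. More than one level is the likelier case under the assumed DLT rates of 10% to 30%, but the documents do not show which path occurred. The counts rest on a full MTD group and complete cohorts.

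The direction and size of any change in AE incidence are unknown. No error rate, power figure or escalation decision is touched, and subject protection is not impaired. The severity is minor to should-fix, and the matter concerns reporting only.

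**What to change.** - In Section 14.3.1, state that the primary AE analysis uses the Section 5.5.1 safety set, tabulated by dose level received and overall with exact confidence intervals, and with the MTD group as its own column.
- In Section 14.2, add that the MTD-only sentence does not apply to safety endpoints.
- Because accrual and the DLT windows have closed, report AE results for both the 5.5.1 set and the MTD-only set, so that neither can be selected after the data are seen.
- State that subjects given only the 15 mCi test dose are outside the safety set, and list their AEs separately.

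The efficacy definition in Section 5.5.1 and the dose-delay summary in Section 14.3.2 can stay as they are.

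The cost is a few sentences, some extra table columns and one listing. No subjects, visits or data are added.

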4 STUDY DESIGN

This is a Phase 1, single center, dose escalation and dose expansion study of subjects with locoregionally recurrent head and neck cancer who may also have distant metastatic disease. All subjects will receive a dosimetry test dose of CLR 131 (flat dose of 15 mCi) to establish drug uptake by the tumor.

Subjects who have tumor uptake of the CLR 131 dosimetry test dose as determined on SPECT/CT imaging by the study radiologist will be eligible to participate on the treatment portion of this clinical trial. Any subject who demonstrates tumor uptake of CLR 131 by SPECT/CT imaging after the test dose will continue to participate in the treatment portion of the study. Up to six participants who do not demonstrate tumor uptake of CLR 131 by SPECT/CT will also continue with the treatment portion of the study. Based on prior experience of subjects receiving CLR 131, 75 % of eligible subjects are estimated to demonstrate CLR 131 uptake within their tumors.

Subjects showing uptake will receive a cumulative tumor dose of 60-70 Gy using personalized dose calculation of CLR 131 (via Monte Carlo) combined with external beam radiation. If the Monte Carlo dose estimate for any subject is greater than 60 Gy for the 2 doses of CLR 131 (highly unlikely based on preliminary data), then no additional external beam dose will be administered.

All subjects will start thyroid-protection medication the day prior to the CLR 131 dosimetry test dose and will continue to take thyroid protection medication for 14 days after the last CLR 131 dose.

Treatment Plan

Enrollment will start at dose level 1. Subjects will receive 2 doses of CLR 131 intravenously with the first dose on day 1 followed by the second dose on day 8. The dose of CLR 131 will be based on the dose escalation schema.

Dose Escalation Schema	
Dose Level	Doses** of CLR 131
-1*	12.5 mCi/m ²
1	15.6 mCi/m ²
2	18.75 mCi/m ²

*Dose level -1 is the de-escalation dose. The first four patients will be given Dose 1. Dose -1 will only be used if toxicities warrant de-escalation.

** Dose level listed is administered first on day 1 and again on day 8.

SPECT/CT imaging will be performed on days 2, 3, 4-6, and 7-8 of the treatment period to visualize and quantitate the biodistribution of CLR 131. Using the SPECT/CT imaging scans, the [name] lab will perform the Monte Carlo calculations to predict absorbed dose of CLR 131 to tumors and normal structures.

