7.1.1 Dosimetry Test Dose

On the day of dosing, prior to infusion, the following tests and procedures will be done:

- Confirm subject is taking thyroid-protection medication as directed
- Urine pregnancy test for WOCP (within 24 hrs prior to the dosimetry test dose)
- Vital signs will be collected prior to and 1 hour post CLR 131 infusion

CLR 131 will be administered through a freely running peripheral IV catheter via a slow infusion of approximately 30 minutes duration. For the dosimetry test dose, the dose of CLR 131 will be a flat dose of 15 mCi.

- SPECT/CT imaging will be performed approximately three days after infusion to assess tumor uptake of CLR 131. If a subject does not demonstrate CLR 131 uptake on the day 3 SPECT/CT scan, then a repeat SPECT/CT can be performed 7 days after the CLR 131 test dose to reassess for uptake.
- Subjects who demonstrate uptake of CLR 131 on either the day 3 or day 7 SPECT/CT scan, along with up to six patients who do not demonstrate uptake of CLR 131 are eligible for the treatment doses of CLR 131.

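### Section 14.2's MTD-only rule is the only population the plan gives for tumor uptake and dosimetry: it drops usable subjects and can, under some conditions, inflate the uptake proportion

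*Combined protocol and SAP*

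**What the plan says.** The analysis population is set by one sentence at the end of Section 14.2: "Statistical analysis for outcomes is based on participants treated at the MTD, including dose escalation patients treated at the MTD". The same paragraph caps that set: "Up to 12 subjects will be treated at the MTD".

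Tumor uptake by SPECT/CT with Monte Carlo calculation is a listed secondary outcome (Section 3.2.2). Its analysis in Section 14.3.2 is a single line: "CLR 131 tumor uptake via SPECT/CT imaging and Monte Carlo calculations will be reported". That line has no denominator, interval or population. Section 5.5.1 defines a safety set and an efficacy set, but none for uptake or dosimetry.

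On how uptake is obtained, Section 4 states: "All subjects will receive a dosimetry test dose of CLR 131 (flat dose of 15 mCi) to establish drug uptake by the tumor". The result then decides who goes on: "Subjects who have tumor uptake of the CLR 131 dosimetry test dose as determined on SPECT/CT imaging by the study radiologist will be eligible". There is a limited exception: "Up to six participants who do not demonstrate tumor uptake of CLR 131 by SPECT/CT will also continue with the treatment portion". The planning value is that "75 % of eligible subjects are estimated to demonstrate CLR 131 uptake within their tumors".

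Quantitative dosimetry is a separate measurement. Sections 6.7.1 and 8.1.12 base it on four SPECT/CT time points after the first treatment dose, whose activity depends on dose level. Section 6.7.1 divides the integrated time-activity fits by injected activity.

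**The concern.** The uptake reading precedes any treatment dose level and follows an identical activity in everyone, so the assigned level cannot affect it. Restricting it to MTD subjects has two consequences.

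- It discards test-dose readings from subjects treated at other levels and from subjects who were never treated.
- The set that remains has been filtered on the endpoint. Every uptake subject may proceed, but only a limited number of no-uptake subjects may. Any distortion is therefore upward.

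The uptake proportion indicates how many patients with recurrent head and neck cancer the approach could serve. It also feeds the accrual reasoning in Section 14.2. It should come from the subjects in whom it was measured.

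**Working it through.** **No plan figure to reproduce.** The documents give no precision or sample-size derivation for uptake. The 75% is an assumption and the 12 is a ceiling.

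**Inputs from the documents.** Planned uptake p = 0.75 (Section 4); at most k = 6 no-uptake places over the whole study (Section 4); MTD set of 12 at most, cohorts of 4, at most 8 per level in escalation with one exception allowing 10 at Dose Level 1 (Section 14.2).

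**Assumptions not in the documents.** Constant uptake probability; MTD set full at 12; m subjects treated off the MTD, with m = 0, 4 or 8 as common paths; off-MTD subjects treated first; alternative values of p and of places used.

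**Step 1: chance that the six places run out.** With X ~ Bin(n, 1 − p) no-uptake subjects among the first n tested, P(X ≥ 7) is:

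| p | n = 12 | n = 16 | n = 20 |
|---|---|---|---|
| 0.75 | 0.014 | 0.080 | 0.214 |
| 0.50 (assumed) | 0.387 | 0.773 | 0.942 |

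**Step 2: expected uptake share in the MTD set.** While places remain, every tested subject is treated; once k are used, only uptake subjects are. The number of no-uptake subjects among the first n treated is therefore distributed as min(k, Xₙ), with Xₙ ~ Bin(n, 1 − p). Then

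expected share = 1 − {E[min(k, Xₘ₊₁₂)] − E[min(k, Xₘ)]} / 12.

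Example with p = 0.75, k = 6, m = 8: 1 − (4.624 − 2.000)/12 = 0.78. Example with p = 0.50, k = 6, m = 4: 1 − (5.844 − 2.000)/12 = 0.68.

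| True uptake p | Places used k | m = 0 | m = 4 | m = 8 |
|---|---|---|---|---|
| 0.75 (plan) | 6 | 0.75 | 0.76 | 0.78 |
| 0.75 | 3 | 0.80 | 0.86 | 0.91 |
| 0.75 | 0 | 1.00 | 1.00 | 1.00 |
| 0.50 (assumed) | 6 | 0.56 | 0.68 | 0.83 |
| 0.90 (assumed) | 6 | 0.90 | 0.90 | 0.90 |

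A simulation of 20,000 runs per setting agrees to within 0.002 in these cells. In the longest path tried (m = 16, p = 0.75, k = 6) the share is 0.86. The increments of E[min(k, Xₙ)] shrink as n grows, so treating off-MTD subjects first gives the largest excess. If MTD subjects come earlier, it is smaller.

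**Step 3: subjects left out.** Expected number tested = (m + 12 − E[min(k, Xₘ₊₁₂)]) / p. With p = 0.75 and k = 6:

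- m = 0: (12 − 2.983)/0.75 = 12.0, so about 0 left out.
- m = 4: (16 − 3.884)/0.75 = 16.2, so about 4 left out.
- m = 8: (20 − 4.624)/0.75 = 20.5, so about 8 left out.

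**Step 4: precision.** Exact (Clopper-Pearson) 95% intervals at an observed 75%:

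- 9/12: 43% to 95%
- 12/16: 48% to 93%
- 15/20: 51% to 91%

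**The case against.** The strongest reply is that the plan never promises an uptake rate. The objective is a dosimetric evaluation (Section 3.1.2), the 75% serves as an accrual input, and no test or decision rule depends on uptake. The MTD sentence also closes a sample-size section about the expansion cohort, while Section 14.3.2 carries no such limit. It may never have been meant for uptake. This stands in part: the plan does not certainly discard these data. But the sentence has no exception, uptake is a listed outcome, and no other population is written down. An analyst following the text would use the MTD set.

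Three stronger readings are tempting, and the documents do not support them.

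- **That the uptake rate is biased upward as a matter of fact.** The six no-uptake places absorb nearly all expected no-uptake subjects at 75%, so the excess there is about 0 to 3 points.
- **That the trial cannot give an unbiased rate.** Every subject is to be test-dosed and scanned, so the proportion in all test-dosed subjects remains computable.
- **That dosimetry is biased in the same way because of the common test dose.** Quantitative dosimetry follows the level-dependent treatment dose. A summary of total Gy at the MTD is defensible, and what is lost is precision.

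The gain in precision is also modest, because all three intervals in Step 4 are wide.

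**Conclusion.** The point holds in a limited form. As written, the plan's only population for uptake and dosimetry is the MTD set. For uptake that set is filtered on the endpoint and omits about 4 to 8 informative subjects on common paths.

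The upward bias is conditional. It is about 0 to 3 points at 75% uptake with the six places filled as they arise and up to 8 subjects treated off the MTD. It becomes material in three situations: true uptake well below plan, many subjects treated off the MTD, or places left unused. The last is possible because the number is a maximum, and Sections 7.2.1.1 and 9 still describe treatment or response assessment as if no-uptake subjects were not treated.

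These sizes rest on the assumed order of treatment, a constant uptake probability, a full MTD set and the chosen off-MTD counts. For dosimetry the finding is lost precision only.

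**What to change.** Amend Sections 14.2 and 14.3.2:

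- Exempt uptake and dosimetry from the MTD-only sentence.
- Define the uptake population as all subjects who received the test dose and had an evaluable SPECT/CT. Report the proportion with an exact confidence interval, beside the 75% planning value.
- Define the dosimetry population as all subjects with SPECT/CT after a treatment dose. Report tumor and organ absorbed dose per unit of injected activity, pooled and by dose level, with total Gy at the MTD in a separate table.

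The cost is wording and a few tables. No added subjects, scans or procedures are needed, because the protocol already schedules the scans and normalises by injected activity. The Protocol Summary records accrual as closed, and uptake readings are known as they arise because they gate treatment. The change should therefore be dated, and the counts tested, with uptake, treated and treated at the MTD should be shown together.
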